6.1.3 Treatment arms/group

This is a single arm study; all participants will receive iptacopan at a dose of 200 mg orally b.i.d.

6.1.4 Treatment duration

The planned duration of the Core treatment period is 24 weeks. If a participant's study treatment is discontinued for any reason, every effort must be made to continue with the study assessments up to Week 24.

An Extension treatment period of 24 weeks is offered to participants who complete the Core treatment period. In the event a participant's study treatment is discontinued during the Extension treatment period for any reason, and if possible, participants should continue with the study assessments up to Week 48.

Please refer to [Section 9.1.1](#) for recommendations for participants who discontinue iptacopan for any reason during the Core or Extension treatment period.

Participants who complete this trial and continue to derive clinical benefit from the treatment based on the investigator's evaluation may join the Rollover extension program (REP).

6.2 Other treatment(s)

6.2.1 Concomitant therapy

All medications, procedures, and significant non-drug therapies (including physical therapy and blood transfusions) administered after the participant was enrolled into the study must be recorded on the appropriate Case Report Forms. Please refer to [Section 8.3.2](#) for the red blood cell transfusions and protocol specific guidelines for its administration.

Each concomitant drug must be individually assessed against all exclusion criteria/prohibited medication during screening period. If in doubt, the investigator should contact the Novartis medical monitor before enrolling a participant or allowing a new medication to be started. If the participant is already enrolled, contact Novartis to determine if the participant should continue participation in the study.

6.2.1.1 Permitted concomitant therapy requiring caution and/or action

Erythropoiesis-stimulating agents (ESAs) and hypoxia inducible factors prolyl hydroxylase inhibitors (HIF-PHIs) are allowed to be used if on stable dose at least 8 weeks before Screening.

During the study, it is recommended to adjust the dose and/or discontinue dosing of ESAs and/or HIF-PHIs based on participant's hemoglobin level as per local guidelines and practice. As a general guide, it is recommended to reduce the ESAs and/or HIF-PHIs dose by 50% if hemoglobin is ≥ 12 g/dL and/or to stop ESAs and/or HIF-PHIs dosing if hemoglobin is ≥ 13 g/dL. Use particular caution in participants with coexisting cardiovascular disease, stroke and chronic kidney disease.

Systemic corticosteroids are allowed to be used for hematological conditions if on stable dose (less than 0.25 mg/kg/d) at least 4 weeks before Screening. During the study, the dose should not be changed during the Core treatment period (up to Day 168 Visit). During the extension treatment period, the dose of systemic corticosteroids can be adjusted based on participant's condition and local guidelines.

Iptacopan has been shown to have a weak inhibition potential for the liver uptake transporter Organic Anion-transporting Polypeptide 1B1 (OATP1B1). Calculation revealed that the exposure (area under the curve (AUC)) of respective sensitive substrates may be increased by <1.5 fold. Although the expected effect on the exposure of respective co-medications is small and may not be clinically relevant, it is recommended to combine iptacopan with sensitive OATP1B1 substrates or those having a narrow therapeutic index (NTI) with caution or apply a staggered dosing (see below). A list of OATP1B1 substrates to be used with caution will be provided to the investigators.

Iptacopan has also been shown to inhibit the efflux-transporter P-glycoprotein (P-gp) on the intestinal level but not the liver. Therefore, direct oral anti-coagulants apixaban, rivaroxaban and edoxaban which are P-gp substrates should be used with caution. For edoxaban a staggered dosing (see below) is recommended in particular for participants with impaired kidney function.

For narrow therapeutic index (NTI) immunosuppressants (e.g. cyclosporine, sirolimus, tacrolimus on a stable dose) which are substrates for the efflux transporter P-gp with no alternative treatment available, a staggered dosing approach is recommended. This can be accomplished by administering the respective co-medication >3 hours following oral administration of iptacopan. Alternatively, compounds with a short T_{max} of around <2 hours (i.e., fast absorption) can be given >1 hour prior to iptacopan. The staggered dosing will avoid increases in systemic exposure of co-administered drugs due to P-gp inhibition by iptacopan at the intestinal level. For participants receiving immunosuppressants (stable dose) and if their exposure is no longer monitored, it is advisable to resume therapeutic drug monitoring after start of treatment with iptacopan (single assessment).

6.2.2 Prohibited medication

Use of the treatments listed below are not allowed during iptacopan administration.

- Any other complement inhibitors, including anti-C5 antibody, are prohibited for the entire study treatment. If anti-C5 antibody is started, the patient should permanently discontinue iptacopan.
- Live vaccines are prohibited for the entire study treatment duration.
- Preclinical studies have shown that systemic disposition of iptacopan is primarily mediated by metabolic clearance, predominantly by CYP2C8 and to a smaller extent by direct glucuronidation. In addition, some contribution from direct renal (approximately 20%) and

direct biliary excretion (around 5 to 10%) is anticipated. iptacopan is also a substrate for the organic anion-transporting polypeptide (OATP) hepatic uptake transporter (see above). To ensure participant safety, co-medications that inhibit multiple disposition mechanisms of iptacopan (e.g. Gemfibrozil) are prohibited. The same applies to strong CYP2C8 inhibitors (main clearance pathway) such as clopidogrel.

- Gemfibrozil (a potent inhibitor of metabolizing enzymes CYP2C8, UGT1A and liver uptake transporter OATP1B1) must be interrupted at least 48 hours before first iptacopan dose until end of iptacopan treatment (and replaced with another appropriate medication used for that indication).
- Strong inhibitors of CYP2C8 such as clopidogrel must be interrupted 7 days before first iptacopan dose until end of iptacopan treatment (and replaced with another appropriate medication).
- Medications that are either “sensitive substrates” for the efflux transporter P-gp or have a narrow therapeutic index (NTI) and are substrates for P-gp should not be administered with iptacopan (interrupted 48 hours before first iptacopan dose). Typical examples are digoxin, quinidine, paclitaxel, fentanyl and phenytoin. However, if no alternative treatment is available, a staggered dosing approach is recommended (refer to [Section 6.2.1.1](#)). The anti-coagulation drug dabigatran which is also a P-gp substrate should not be used in combination with iptacopan and a staggered dosing is also not recommended.

Concomitant medication listed under exclusion criterion 16 is prohibited if not on a stable regimen prior to Screening, for the time periods indicated.

6.2.3 Rescue medication

Rescue medication is allowed to treat serious complications such as thrombosis with anti-thrombotic treatment and management of this complication as per local guidelines and practice. For significant breakthrough hemolysis requiring rescue medication in the opinion of the investigator, rescue medication is allowed and should be managed as per local guidelines and practice.

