In countries where anti-C5 antibody therapy is not available, therapy focuses on managing the clinical manifestations of PNH but do not target the underlying pathophysiology and have little impact on long-term outcomes in PNH patients (Risitano and Rotoli 2008). Hemolysis and anemia in PNH are treated with corticosteroids, androgens (for both chronic and acute hemolysis) and transfusions. Patients are usually given iron supplements, folate and vitamin B12 as supportive therapy for the increased erythropoiesis (Parker et al 2005). When PNH is associated with other bone marrow diseases such as aplastic anemia, immunosuppressive therapy has also been used (Risitano and Rotoli 2008). As thromboembolism is leading cause of death in PNH, anticoagulant therapy is used as a prophylaxis as well as in acute setting. Hematopoietic stem cell transplantation remains the only curative option, however its use is limited to specific cases due to the increased morbidity and mortality (De Latour et al 2012). With such supportive therapies, the median survival rate was approximately 10 years. Therefore, there is a high-unmet medical need for effective and targeted therapies addressing the underlying pathophysiology in PNH patients where anti-C5 is not available (Hillmen et al 1995, Socie et al 1996, De Latour et al 2008).

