14. History of malignancy of any organ system (other than localized basal cell carcinoma of the skin or in situ cervical cancer), treated or untreated, within the past 5 years, regardless of whether there is evidence of local recurrence or metastases.
15. Any medical condition deemed likely to interfere with the patient's participation in the study.
16. Concomitant use of any of the following medications is prohibited if not on a stable regimen for the time period indicated below prior to Screening and those listed in [Section 6.2.2](#):
 - Erythropoiesis-stimulating agents (ESAs) for at least 8 weeks.
 - Any immunosuppressants for at least 8 weeks.
 - Systemic corticosteroids given for hematological conditions (less than 0.25 mg/kg/d) for at least 4 weeks (see [Section 6.2.1.1](#) during the Core treatment period).
 - Vitamin K antagonists (e.g., warfarin) with a stable international normalized ratio (INR) for at least 4 weeks.
 - Low-molecular-weight heparin, and the direct oral anticoagulants rivaroxaban, apixaban and edoxaban, for at least 4 weeks.
 - Iron supplements, vitamin B12, or folic acid for at least 4 weeks.
 - Hypoxia-inducible factor prolyl hydroxylase inhibitors (HIF-PHIs) such as roxadustat for at least 8 weeks.
 - Androgens for at least 4 weeks.
17. Female patients who are pregnant or breastfeeding, or intending to conceive during the course of the study.
18. Women of child-bearing potential, defined as all women physiologically capable of becoming pregnant, unless they are using effective methods of contraception during dosing of investigational drug and for 1 week after stopping of investigational drug. Effective contraception methods include:
 - Total abstinence (when this is in line with the preferred and usual lifestyle of the participant). Periodic abstinence (e.g., calendar, ovulation, symptothermal, post-ovulation methods) and withdrawal are not acceptable methods of contraception.

- Female sterilization (have had surgical bilateral oophorectomy with or without hysterectomy), total hysterectomy or bilateral tubal ligation at least six weeks before taking investigational drug. In case of oophorectomy alone, only when the reproductive status of the woman has been confirmed by follow up hormone level assessment.
- Male sterilization (at least 6 months prior to screening). For female participants on the study, the vasectomized male partner should be the sole partner for that participant.

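### Protocol 6.2.3 leaves rescue to local practice, 6.2.1.1 and 6.2.2 restrict some of the same drugs with no rescue exemption, and SAP 2.5.5 counts rescue by the site's label alone

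*Protocol*

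**What the plan says.** Protocol 6.2.3 allows anti-thrombotic treatment for thrombosis. For BTH that the investigator considers in need of rescue, it adds that "rescue medication is allowed and should be managed as per local guidelines and practice". It names no agent for BTH and does not refer to 6.2.1.1 or 6.2.2.

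Protocol 6.2.1.1 sets the entry condition: "Systemic corticosteroids are allowed to be used for hematological conditions if on stable dose (less than 0.25 mg/kg/d) at least 4 weeks before Screening". It then says "the dose should not be changed during the Core treatment period (up to Day 168 Visit"; adjustment is allowed in the Extension period.

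Protocol 6.2.2 opens with "Use of the treatments listed below are not allowed during iptacopan administration" and closes with "Concomitant medication listed under exclusion criterion 16 is prohibited if not on a stable regimen prior to Screening, for the time periods indicated". Criterion 16 in section 5.2 includes "Systemic corticosteroids given for hematological conditions (less than 0.25 mg/kg/d) for at least 4 weeks". It also lists androgens, immunosuppressants, vitamin K antagonists, low-molecular-weight heparin and three direct oral anticoagulants.

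Protocol 9.1.1 lists corticosteroids among the supportive treatments to consider if serious hemolysis follows iptacopan discontinuation. It applies the same list to participants who taper iptacopan over 14 days.

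Protocol 12.4.6 and SAP 2.5.5 define a supplementary estimand in which rescue use counts as treatment failure, from Day 1 to Day 168 in the SAP. SAP 2.5.5 identifies rescue only by what the investigator enters under the rescue subcategory of the CRF pages for concomitant medication and for procedures.

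**The concern.** The overlap is foreseeable. On management where anti-C5 antibodies are not available, Protocol 1.1 says "Hemolysis and anemia in PNH are treated with corticosteroids, androgens (for both chronic and acute hemolysis) and transfusions", and section 4.1 presents this trial as pivotal for registration in such countries. Local practice for BTH may therefore be a drug that 6.2.1.1 or 6.2.2 restricts.

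Two things are at stake. Sites have no single instruction for an acute event, so care may differ between them. The same course of treatment may also be entered as rescue at one site, which makes the participant a failure under SAP 2.5.5, and as a concomitant-medication deviation at another, which leaves the participant's response status as it was. The supplementary estimand is meant to show what happens when rescue use counts as failure. Its result should not depend on which section a site happened to read.

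**Working it through.** The core of the check is a comparison of text. Each way of treating the event is set against the sections that bear on it.

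| Treatment in the Core period | 6.2.3 or 9.1.1 | 6.2.1.1 | 6.2.2 with criterion 16 | Result |
|---|---|---|---|---|
| Corticosteroid newly started for BTH, on iptacopan | open (6.2.3) | permits only a stable pre-Screening dose | prohibited | conflict |
| Existing corticosteroid dose raised for BTH | open (6.2.3) | dose should not change to Day 168 | regimen was stable before Screening | conflict with 6.2.1.1 |
| Androgen or immunosuppressant newly started for BTH, on iptacopan | open (6.2.3) | no equivalent dose rule | prohibited | conflict |
| Criterion 16 anticoagulant newly started for thrombosis, on iptacopan | open (6.2.3) | no equivalent dose rule | prohibited | conflict |
| New corticosteroid for serious hemolysis during the taper | to be considered (9.1.1) | as in row 1 | iptacopan still being given, so prohibited | conflict |
| Existing corticosteroid dose raised after iptacopan has stopped, before Day 168 | to be considered (9.1.1) | no off-treatment exception | no longer applies | conflict with 6.2.1.1 |
| Transfusion | provided for in 8.3.2 | not restricted | not restricted | none |
| Agent outside criterion 16 and the 6.2.2 list | open (6.2.3) | not restricted | not restricted | none |

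None of 6.2.1.1, 6.2.2, 6.2.3 or 9.1.1 contains an exemption for rescue or an order of precedence.

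Next, which analyses can move:

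- Primary estimand (Protocol 2.1 and 12.4.3; SAP 1.2.1 and 2.5.1): rescue medication is not among the listed intercurrent events, and the responder rule does not use the rescue label.
- The 15% comparison (SAP 2.5.2.2) uses the primary analysis only.
- Analysis sets (SAP 5.2.3): no protocol deviation removes a participant from any set.
- Supplementary estimand (SAP 2.5.5): depends directly on the CRF rescue label.

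Size of the movement, with the planned N of about 40:

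- SAP 5.2.2.2 shows that the marginal proportion from the logistic model equals the simple proportion, so one changed classification moves the estimate from R/40 to (R − 1)/40.
- The difference is 1/40 = 0.025, or 2.5 percentage points.
- This is a maximum. A participant who already fails, by receiving a transfusion or meeting the transfusion criteria between Day 14 and Day 168, or by missing the hemoglobin criterion, contributes 0 under either label. A participant who responds in only some imputed datasets contributes less than 2.5 points.
- For k otherwise-responding participants labelled differently, the maximum is k × 2.5 points. The documents give no value for k.

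**The case against.** The best defence is that the sections can be read together. The protocol glossary mentions concomitant and rescue therapy as separate kinds of other treatment. The corticosteroid rule sits under permitted concomitant therapy, the closing line of 6.2.2 speaks of concomitant medication, and rescue has its own section. Section 6.2.3 expressly allows anti-thrombotic treatment although criterion 16 lists anticoagulants, which suggests that it was meant as a specific permission alongside general limits. The corticosteroid rule is worded as a recommendation. Section 6.2.1 also tells investigators in doubt to contact the sponsor's medical monitor before allowing a new medication, so sites are not left to choose alone.

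This softens the point but does not remove it. The exemption has to be inferred, since no sentence states it. SAP 2.4.2 points the other way by summarising rescue medications among the concomitant medications. The medical monitor route deals with individual queries and does not standardise the CRF label.

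A reader might infer that any site treating BTH must breach one of the sections. The documents do not support that: the sentence in 1.1 that names corticosteroids and androgens also names transfusion, which 8.3.2 provides for from Day 1 and neither 6.2.1.1 nor 6.2.2 restricts. A reader might also take the problem to stop at corticosteroids and androgens given for hemolysis. Criterion 16 extends it to anticoagulants.

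It is also fair to say that widening the SAP derivation partly replaces the investigator's opinion, on which 6.2.3 rests, with a rule based on drug and indication. That is a real change of definition and should be stated as one.

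**Conclusion.** The conflict is real but limited to the cases marked in the table. It rests on the literal wording of the four protocol sections and on the absence of any stated exemption.

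Its statistical reach is one supplementary estimand, by at most 2.5 points per otherwise-responding participant whose treatment is labelled differently. It is tempting to turn this into a total: 2 to 4 such participants would give 5 to 10 points. The documents supply no such count, and the total would also require every one of them to be an otherwise-responder and all to be labelled one way rather than the other. Nor do the documents support a threat to the primary result, because the primary analysis, the 15% comparison and the analysis sets do not use the rescue label.

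The clarification is still worth making. It is cheap, it gives sites one instruction in an acute event, and it keeps the supplementary estimand from depending on labelling.

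**What to change.** **Protocol.** Reconcile 6.2.1.1, 6.2.2, 6.2.3 and 9.1.1 by stating whether rescue use, and the supportive treatment listed in 9.1.1, is exempt from the concomitant-medication limits. Which clinical rule should apply is for the sponsor to decide; none is proposed here.

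**SAP 2.5.5.** Count as rescue the CRF rescue subcategory plus any criterion 16 medication started or increased between Day 1 and Day 168 with BTH or thrombosis as the recorded indication, whichever label the site used. This assumes that the CRF captures an indication for each medication, which the documents reviewed do not state.

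**Cost.** One clarification at the next protocol amendment and one more derivation line in the SAP. The supplementary response rate may come out slightly lower, because the wider definition can only add failures.

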6.3 Participant numbering, treatment assignment, randomization

6.3.1 Participant numbering

Each participant is identified in the study by a Participant Number (Participant No.), that is assigned when the participant is enrolled for screening and is retained for the participant throughout his/her participation in the trial. A new Participant No. will be assigned at every subsequent enrollment if the participant is re-screened. The Participant No. consists of the Center Number (Center No.) (as assigned by Novartis to the investigative site) with a sequential participant number suffixed to it, so that each participant’s participation is numbered uniquely across the entire database. Upon signing the ICF, the participant is assigned to the next sequential Participant No. available.

A new ICF will need to be signed if the investigator chooses to re-screen the participant after a participant has screen failed, and the participant will be assigned a new Participant No.

6.3.2 Treatment assignment, randomization

No randomization will be performed in this study.

All eligible participants will be assigned medication kits via Interactive Response Technology (IRT). The investigator or his/her delegate will contact the IRT after confirming that the participant fulfills all the inclusion/exclusion criteria. The IRT will assign a unique medication number for the first package of study treatment (iptacopan) to be dispensed to the participant.

6.4 Treatment blinding

Treatment will be open to participants, Novartis Clinical Trial Team (CTT), the investigator staffs and persons performing the assessments. The CTT will have access to standard reports of patient profiles and other listings necessary to fulfill data review. There will be an Independent Statistician and an Independent Programmer who will provide analyses of safety data for the review of the members of the DMC at periodic intervals.

6.5 Dose escalation and dose modification

Iptacopan will be administered at a dose of 200 mg b.i.d. Dose adjustments and/or interruptions are not planned.

6.6 Additional treatment guidance

6.6.1 Treatment compliance

The investigator must promote compliance by instructing the participant to take the study treatment exactly as prescribed and by explaining that compliance is necessary for the participant's safety and the validity of the study. The participant must also be instructed to contact the investigator if he/she is unable for any reason to take the study treatment as prescribed.

Compliance with iptacopan will be assessed by the investigator and/or study personnel at each visit using capsule counts and information provided by the participant. This information should be captured in the source document at each visit.

Participants will be given the opportunity to use a generic reminder application (app) that will synchronize with the participant mobile phone calendar to remind participants to take their medication. The participants may choose to report compliance to the study site staff through the app. The use of this application and the compliance reporting feature are entirely voluntary and not mandated for use.

All study treatment dispensed and returned must be recorded in the Drug Accountability Log.

6.6.2 Recommended treatment of adverse events

The participants and treating staff need to be instructed to be vigilant for any clinical signs of bacterial infections (e.g., malaise, chills, fever, nausea, photophobia, generalized muscle and joint pain) and to measure the body temperature at minimum at the times of symptoms of presumed infection. Participants will be instructed to contact the study physician immediately

in case of suspicion of infection or elevated body temperature ($> 38.3^{\circ}\text{C}$ by oral or tympanic method) for a 'phone directed triage.

In case of a suspected bacterial infection, participants should be immediately considered for emergency evaluation and empirically treated with an appropriate antibiotic course.

In case of any (bacterial and non-bacterial incl. COVID-19) severe infection, interruption of iptacopan dosing could be considered, on a case-by-case basis. However, every effort should be taken to keep the participant on study treatment unless the risk outweighs the benefit in the opinion of the investigator.

If iptacopan treatment is to be permanently discontinued, please refer to [Section 9.1.1](#) for the appropriate actions.

Medication used to treat adverse events (AEs) must be recorded on the appropriate case report form (CRF).

LNP023 (Iptacopan) Participant Safety Card

All participants will be provided with a Participant Safety Card. Participants will be instructed to be vigilant for any clinical sign or symptom of infection and to contact the investigator or local physician immediately. In case of suspicion of bacterial infection, further evaluation should be initiated and antibiotic treatment should be started as soon as possible.

